7.7 Potential Drug-Induced Liver Injury (DILI)

Wherever possible, timely confirmation of initial liver-related laboratory abnormalities should occur prior to the reporting of a potential DILI event. All occurrences of potential DILIs, meeting the defined criteria, must be reported as SAEs (7.3.1 for reporting details).

Potential drug induced liver injury is defined as

1. AT (ALT or AST) elevation > 3 times upper limit of normal (ULN)

AND

2. Total bilirubin > 2 times ULN, without initial findings of cholestasis (elevated serum alkaline phosphatase),

AND

3. No other immediately apparent possible causes of AT elevation and hyperbilirubinemia, including, but not limited to, viral hepatitis, pre-existing chronic or acute liver disease, or the administration of other drug(s) known to be hepatotoxic.

7.8 Other Safety Considerations

Any significant worsening noted during interim or final physical examinations, electrocardiograms, x-rays, and any other potential safety assessments, whether or not these

procedures are required by the protocol, should also be recorded as a nonserious or serious AE, as appropriate, and reported accordingly.

8 STATISTICAL CONSIDERATIONS

8.1 Sample size determination

Sample size is calculated using SigmaPlot software (San Jose, CA). For the two major outcome variables i.e. myocardial fat and hepatic fat, the sample size of ~ 16 patients per treatment group (total of 32 patients) will have >90% power to detect a difference in the means of 20%, assuming a standard deviation of 15%, and with $\alpha = 0.025$. Given that we expect about 20% of the patients enrolled may not complete the 6 month study, we would like to enroll 40 patients so that 32 patients may complete the study.

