Statistics:	Between groups (i.e., saxagliptin therapy vs. placebo) comparisons will be made using two-way analysis of variance (ANOVA). Pre and post treatment within a group will be analyzed using paired t-tests. Simple correlation analysis will be performed with Pearson's correlation coefficients to examine the relationship between hepatic fat and myocardial fat and LV function. Multivariate analysis will be performed where appropriate to examine the impact of simultaneous changes (glucose levels) in experimental parameters on hepatic fat. All statistical analysis will be performed using SAS (Cary, NC). Sample size is calculated using SigmaPlot software (San Jose, CA). For the two major outcome variables i.e. myocardial fat and hepatic fat, the sample size of ~ 16 patients per treatment group (total of 32 patients) will have >90% power to detect a difference in the means of 20%, assuming a standard deviation of 15%, and with alpha= 0.025. Given that we expect about 10-15% of the patients enrolled may not complete the 6 month study, we would like to enroll 36 patients so that 32 patients may complete the study.

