CRP, IL-1, IL6, TNF-alpha, MMP-9, ICAM, VCAM, Fibroblast Growth Factor 21 (FGF21), FFA, insulin, LPS and LPS-BP. Liver and Myocardial fat and LV function as well as monocyte studies for inflammatory pathways as detailed previously will be repeated after 26 weeks of therapy.

Measurement of Liver Fat Content (MR Spectroscopy)

Localized ¹H nuclear magnetic resonance spectra of the liver will be obtained on a 3.0 Tesla magnetic resonance imaging scanner (Department of Radiology, St Lukes Episcopal Hospital and Texas Heart Institute, Houston) using a standard body coil in transmitter and receiver mode. An initial T1-weighted spin-echo anatomical magnetic resonance scan for liver MRS localization will be performed with the following parameters: repetition time/echo time = 130 msec/15 msec; 160 degrees; slice thickness = 7 mm; field of view = 44 cm x 45 cm; number of excitations = 1; and an image matrix = 100 x 256. The slice with the largest gross dimensions of the liver will be chosen for the MRS study. MRS for water and fat quantification will be accomplished by using a point resolved spectroscopy sequence as described previously (3). The imaging parameters for point resolved spectroscopy sequence are as follows: repetition time/echo time = 1500 msec/54 msec; 90 degree; number of averages = 2; and data points = 512. A 3 cm x 3 cm x 3 cm volume (voxel) will be selected in the left, right anterior, and right posterior hepatic lobes for scanning to provide a more generalized distribution of fat within the liver. During the measurements, the

subject will be supine within the bore of the magnet. The total scan time is approximately 60 min. During the MRS examinations, identical areas of the liver are scanned in the pre- and post-treatment MRS studies of the same subject by the use of anatomical landmarks visualizing images.

After line broadening, phase and baseline correction, the peak area of the water at 4.77 ppm, and fat resonance (Sf) at 1.4 ppm will be measured. Quantification of the fat content will be done by comparing the area of the Sf with that of the unsuppressed water. Spectroscopic data will be processed using the operating system software. Hepatic fat percentage will be calculated by dividing $(100 \times \text{Sf})$ by the sum of Sf and peak area of the water. This technique is highly reproducible, with a coefficient of variation less than 2% when the same subjects were studied on eight separate days.

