8.4 Analyses

8.4.1 Demographic and baseline characteristics : Demographic and baseline characteristics will be summarised using summary statistics based on the ITT data set, for each treatment group as well as for all patients combined. Key baseline characteristics will be summarised. No statistical test will be performed for comparison of any baseline measurement among treatment groups. Demographic and baseline characteristics will be summarised for the total study population.

8.4.2 Efficacy Analysis: Between groups comparisons will be made using two-way analysis of variance (ANOVA.) to analyze changes in hepatic/myocardial fat following saxagliptin

treatment in comparison to placebo (primary efficacy analysis). Secondary efficacy analysis will include the effect of saxagliptin (versus placebo) on LV function and monocyte inflammation. Pre and post treatment within a group will be analyzed using paired t-tests. Simple correlation analysis will be performed with Pearson's correlation coefficients to examine the relationship between hepatic fat and myocardial fat/ LV function . Spearman Rank Correlation will be used for data which is not normally distributed. All statistical analysis will be performed using SAS (Cary, NC).

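### The 20% difference and 15% SD in section 8.1 have no stated scale, and the primary two-way ANOVA names no scale for change and does not adjust for baseline fat, so the >90% power is not tied to the planned test

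*Combined protocol and SAP*

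**What the plan says.** - **Sample size (section 8.1; the synopsis gives the same inputs).** For myocardial and hepatic fat together, about 16 patients per group "will have >90% power to detect a difference in the means of 20%, assuming a standard deviation of 15" percent. The synopsis has "assuming a standard deviation of 15%, and with alpha= 0.025". Neither place says whether 20% and 15% are relative changes or percentage points, whether the SD is of values or of changes, or whether alpha is one- or two-sided.
- **Measurement (section 4.1).** Liver fat is in percent of signal: "Hepatic fat percentage will be calculated by dividing" the fat peak, times 100, by the sum of the fat and water peaks. The myocardial triglyceride subsection gives acquisition settings but no formula or unit for the result.
- **Endpoint (section 8.3).** A reduction in hepatic and myocardial fat relative to placebo. No scale is given.
- **Primary analysis (section 8.4.2).** A two-way ANOVA "to analyze changes in hepatic/myocardial fat following saxagliptin" compared with placebo. The factors are not named, the kind of change is not defined, and no baseline covariate is listed.
- **Non-normal data (section 8.4.2).** The only provision is "Spearman Rank Correlation will be used for data which is not normally distributed". It concerns the correlation analyses, not the primary comparison.

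**The concern.** A single pair of figures for two organs, one of them without a stated unit, reads most naturally as relative change. A two-way ANOVA of pre- and post-treatment data reads most naturally as treatment by time on the measured values, which tests the difference in absolute change. If both readings are right, the power calculation and the test are on different scales.

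Under a proportional effect, absolute change grows with baseline fat. Patients with much fat then dominate the variance, and an SD of 15% no longer describes the analysed variable. The eligibility criteria (sections 4.2.1 and 4.2.2) restrict BMI to 30-35 but set no limits on liver or heart fat, so the design does not bound the baseline spread directly.

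Two things are at stake. The power margin is thin. And section 8.4.2 permits absolute, percent or log change, which can give different p-values in 32 patients, so the scale could be chosen after the data are seen.

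**Working it through.** **1. Reproduce the plan's figure.** Inputs from section 8.1: n = 16 per arm, difference 20, SD 15, alpha 0.025 (taken as two-sided, an assumption).

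- Standardised effect: 20/15 = 1.333.
- Noncentrality: 20 / (15 × √(2/16)) = 3.77, with 30 df.
- Exact two-sided t power: 0.9145. The normal approximation gives 0.937, and a one-sided exact test 0.954.
- With 15 per arm the exact two-sided power is 0.893, so 16 is the smallest number above 90%.

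The stated power is confirmed. At 16 per arm, 90% power needs a standardised effect of at least 1.30 on whichever scale is analysed.

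**2. Scales on which it carries over.** The calculation uses only the ratio 20/15.

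- Percent change, with 20 and 15 as relative figures: 0.9145.
- Absolute change, with 20 and 15 as percentage points: 0.9145.
- Log change: about 91% if the SD of relative change is 15%. If instead the log SD is 0.15, the effect is −ln(0.8)/0.15 = 0.223/0.15 = 1.49 and power is 0.963.

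**3. Relative inputs, absolute change analysed.** Assumptions not in the documents: baseline fat is log-normal with mean 1 and CV c, and independent of relative change; relative change has mean 0 on placebo and −0.20 on saxagliptin, SD 0.15 in both arms.

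- Variance of absolute change, placebo: (1 + c²) × 0.0225.
- Variance, saxagliptin: (1 + c²) × (0.0225 + 0.04) − 0.04.
- Standardised effect: 0.20 / √(mean of the two variances).

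For c = 0.5: placebo 1.25 × 0.0225 = 0.0281; saxagliptin 1.25 × 0.0625 − 0.04 = 0.0381; mean 0.0331; effect 0.20/0.182 = 1.10, below the 1.30 needed.

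The data are skewed, so power was taken from simulation (20,000 to 40,000 trials per setting, two-sample t-test, two-sided 0.025). Where a range is shown, repeated runs differed by about one point.

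| Baseline CV (assumed) | Standardised effect | Power, absolute change | Power, percent or log change |
|---|---|---|---|
| 0 | 1.33 | 91-92% | about 91% |
| 0.25 | 1.26 | 88-89% | about 91% |
| 0.5 | 1.10 | 80-81% | about 91% |
| 0.75 | 0.93 | 69-70% | about 91% |
| 1.0 | 0.78 | 58-59% | about 91% |

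At CV 0.1 and 0.2 the absolute-change power is 91% and 90%, so the loss is small there.

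**4. Effect of baseline adjustment.** Same model, absolute change, CV 0.75: adding baseline fat as covariate raises power from 69% to 75%. If both arms also fall by 10%, for instance through the diet instruction given to everyone, unadjusted power is 55% and adjusted power 75%. Where baseline carries no information, adjustment costs about one point.

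**The case against.** The strongest reply is that no contradiction has been shown. Section 8.4.2 never says absolute change. If changes there means percent change, sections 8.1 and 8.4.2 agree and power is 91%. The losses in the table need relative inputs, an absolute-scale analysis, a proportional effect, a log-normal baseline and a chosen CV, none of which the documents give. This stands: the table shows what the open wording allows, not what will happen.

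A reader might infer that the >90% power holds only if the outcome is log-transformed. The documents do not support that, since percent change does equally well, and so does absolute change if the figures are percentage points. The ordering can also reverse. With an additive effect (20 units, SD 15, baseline mean 100, log-normal, values floored at 1), absolute change keeps 90-91%, while log change falls to 85, 64, 51 and 48% at CVs of 0.25, 0.5, 0.75 and 1.0. The log scale is a modelling choice, and it is sensitive to values near zero.

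A reader might also take both outcomes to be percentages. That is documented for hepatic fat only.

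The reply does not remove two things. The plan leaves the scale of its primary test open, and it makes no use of a baseline measurement that every patient has.

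**Conclusion.** The point holds as a gap between the power statement and the primary analysis, not as an error of arithmetic. Section 8.1 is right as a calculation (91%, two-sided), but nothing ties its inputs to the variable that section 8.4.2 analyses. To conclude that the primary test lacks its stated power would go further than the documents allow.

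If the inputs are relative and measured values are analysed, the shortfall runs from about 2 points at a baseline CV of 0.25 to more than 30 points at a CV of 1.0. That rests on the assumed proportional effect and log-normal baseline. The case for adjusting for baseline does not depend on settling the scale: the gain can be material and the cost is about one point. Adjustment does not cure a wrong scale, since it reaches only 75% at a CV of 0.75 on absolute change, so both changes are needed. This should be corrected before unblinding.

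**What to change.** - **Section 8.1 and the synopsis:** state for each outcome whether 20% and 15% are relative changes or percentage points, say that the SD is that of the change, and justify it on that scale. Give the unit of myocardial fat.
- **Sections 8.3 and 8.4.2:** define each primary outcome as change from baseline to week 26 on that same scale. Replace the unadjusted two-way ANOVA with an ANCOVA comparing the arms, with the baseline value of that fat measure as covariate.
- **If the figures are relative:** change in log fat with log baseline as covariate is a suitable choice, reported as a ratio of geometric means with its confidence interval. Give absolute change as a sensitivity analysis.

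The cost is wording only, with no added patients, visits or scans. The covariate uses one degree of freedom. If baseline proves uninformative, that takes about one point from a 91% power that has little to spare. On the log scale, a rule for near-zero values must be fixed in advance, because an arbitrary offset can influence the result.

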8.2 Population for analysis

All patients used in the analyses of the primary and secondary objectives will belong to the intention-to-treat (ITT) population. This population is defined as all randomised patients. The patients will be analysed according to the treatment group to which they were randomized.

8.3 Endpoint Definitions:

Primary Efficacy Endpoint: is defined as the effect of saxagliptin compared with placebo on reduction in hepatic and myocardial fat.

Secondary Efficacy endpoint: is defined as the effect of saxagliptin compared with placebo on improvement in left ventricular systolic and diastolic function and a reduction in monocyte inflammation.

Safety endpoints: The number and percent of patients with an AE will be summarised for each treatment group. In addition, the number and percent of patients with a predefined marked abnormality in clinical laboratory tests will be summarised by treatment group.

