6.4 Efficacy Assessments

6.4.1 Primary Efficacy Assessment

The primary efficacy objective is to determine whether treatment with saxagliptin compared with placebo will result in a reduction in hepatic and myocardial fat in patient with IGT.

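### Hepatic and myocardial fat are sized at alpha 0.025, but the analysis sections give no test level, sidedness or either/both rule; Holm at overall 0.05 would close the gap with more power and no extra patients

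*Combined protocol and SAP*

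**What the plan says.** Section 8.1 sizes two outcomes together: "For the two major outcome variables i.e. myocardial fat and hepatic fat, the sample size of ~ 16 patients per treatment group", 32 completers in all. It states more than 90% power for a 20% difference in means. The synopsis gives the same basis, "assuming a standard deviation of 15%, and with alpha= 0.025". This 0.025 is the only significance level in the documents. They do not say whether it is one- or two-sided, or that it is half of 0.05.

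Three later places describe the primary comparison:

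- Section 6.4.1 asks "whether treatment with saxagliptin compared with placebo will result in a reduction in hepatic and myocardial fat in patient with IGT".
- Section 8.3 states: "Primary Efficacy Endpoint: is defined as the effect of saxagliptin compared with placebo on reduction in hepatic and myocardial fat".
- Section 8.4.2 states: "Between groups comparisons will be made using two-way analysis of variance", used "to analyze changes in hepatic/myocardial fat following saxagliptin" treatment against placebo.

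None of the three gives a test level, a sidedness, a multiplicity method, or a rule on whether one outcome or both must succeed. The wording points both ways. The conjunction in 6.4.1 and 8.3 suggests that both are needed, while the slash in 8.4.2 and the 0.025 in 8.1 suggest two separate claims.

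**The concern.** With two primary outcomes, the trial's conclusion can turn on a rule that is not written down. Suppose the two p-values are 0.01 and 0.04:

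- 0.025 for each: one outcome is supported.
- Holm at overall 0.05: both are supported.
- Both required at 0.05: success.
- Both required at 0.025: failure.

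A rule chosen after the data are seen would be open to challenge. Two things are at stake. One is error control: an analyst who finds no level in 8.4.2 might use 0.05 for each outcome and claim whichever succeeds. The other is power: if the split implied by 8.1 is applied as a fixed 0.025 each, the trial gives up power that a stepwise test would recover at no cost in patients.

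**Working it through.** **Inputs.** From 8.1 and the synopsis: 16 per arm, difference 20, SD 15, alpha 0.025, two outcomes. Assumed, because the documents do not say: 15 is the SD of the analysed change, the same effect holds for both outcomes, and the outcomes correlate between 0 and 0.8. Section 8.4.2 does not name the ANOVA factors. If it is treatment by time with repeated measures, the interaction F on 1 and 30 df is the square of the two-sample t on change, so t-test power applies.

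**Step 1: the plan's own figure.** Noncentrality = 20 / (15 × √(2/16)) = 20 / 5.303 = 3.771, with 30 df.

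- Two-sided 0.025 (critical t 2.360): power 91.5%. With 15 per arm it is 89.3%, so 16 is the smallest number above 90%.
- One-sided 0.025, the same as two-sided 0.05 (critical t 2.042): power 95.4%. Here 13 per arm would suffice (90.3%; 12 gives 87.7%).

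The stated figure is reproduced. Both readings satisfy it, but 16 fits two-sided 0.025 better.

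**Step 2: error if no split is applied.** For independent outcomes and an either-outcome claim:

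- 0.05 each: 1 − 0.95² = 9.75%.
- 0.025 each: 1 − 0.975² = 4.94%.

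**Step 3: power at correlation 0, both outcomes responding.** Let a = 0.9145 (power at 0.025) and b = 0.9543 (power at 0.05). Holm tests the smaller p-value against 0.025 and, only if that is met, the other against 0.05.

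- Both, 0.025 each: a² = 83.6%.
- Both, Holm: b² − (b − a)² = 0.9107 − 0.0016 = 90.9%.
- Both required at 0.05: b² = 91.1%.
- One given outcome, Holm: a + (b − a) × a = 0.9145 + 0.0364 = 95.1%.
- At least one, 0.025 each or Holm: 1 − (1 − a)² = 99.3%.

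**Step 4: other correlations.** Simulated bivariate normal data, 16 per arm, two-sided t-tests, 1,000,000 runs per setting:

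| Correlation | Both, 0.025 each | Both, Holm | Both required at 0.05 | Per outcome, Holm | At least one (0.025 each or Holm) |
|---|---|---|---|---|---|
| 0 | 83.7% | 90.9% | 91.1% | 95.1% | 99.3% |
| 0.3 | 84.5% | 91.2% | 91.5% | 94.8% | 98.4% |
| 0.5 | 85.4% | 91.5% | 91.9% | 94.5% | 97.5% |
| 0.8 | 87.4% | 92.3% | 93.0% | 93.9% | 95.5% |

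With no effect on either outcome, the chance of any false claim is the same under 0.025 each and Holm: 4.0% to 5.0%.

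**Step 5: only one outcome responds.** At correlation 0, Holm's power for the responder is a + (b − a) × 0.025 = 91.6%, against 91.5%. The false-positive rate for the other outcome is 0.025 + 0.025 × a = 4.8%, against 2.5%. At correlation 0.8 it is 4.3%.

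**Step 6: meaning of the SD.** If 15 were the SD at a single visit, with pre/post correlation r, the SD of change would be 15 × √(2(1 − r)).

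- r = 0.3: SD 17.7, power 79.1% per outcome. For independent outcomes, power for both is 62.6% at 0.025 each and 75.0% by Holm.
- r = 0.8: SD 9.5, power above 99.9%, and Holm adds almost nothing.

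**The case against.** The strongest case against is that Holm is a preference. Testing each outcome at 0.025 is valid, its 91.5% per-outcome power meets the stated target, and the plan sets no target for winning on both. Holm leaves power for at least one outcome unchanged, adds almost nothing if only one outcome responds, and has no simple matching simultaneous intervals. All of that is true. What remains is that Holm rejects whenever 0.025 each does, keeps the same familywise bound and needs no more patients, so an outcome-by-outcome claim loses no power by using it.

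It can also be said that the two-sided split is not in the text. That stands too. The plan says approximately 16, one-sided 0.025 also gives more than 90%, and the endpoint is worded as a reduction, which is directional. The split is the better-fitting reading, not an established one.

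Two stronger readings are tempting, and the documents support neither. A reader might infer that the trial has uncontrolled type I error near 10%. That figure holds only if someone tests each outcome at 0.05 and claims either; nothing in the plan says so, and the 0.025 in 8.1 points the other way. A reader might also infer that the trial is too small because power for both outcomes is below 90% at 0.025 each. The sample size reproduces for a single outcome, and no joint-power goal is stated.

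**Conclusion.** The point holds as a gap in the decision rule with a cheap improvement attached; it is not an error in the sample size. That the level, the sidedness and the either/both rule are missing from 6.4.1, 8.3 and 8.4.2 is certain from the text. That 0.025 is half of a two-sided 0.05 is likely but inferred.

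If claims are made outcome by outcome and both outcomes respond at the design effect, Holm adds about 5 to 7 percentage points of power for both and about 2 to 4 points per outcome. These sizes rest on 15% being the SD of the analysed change and on a correlation between 0 and 0.8. Under the single-visit readings of the SD tried above (pre/post correlation 0.3 to 0.8, independent outcomes), the gain for both runs from about 12 points to almost none. The choice should be settled before unblinding, since the same pair of p-values can lead to different conclusions.

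**What to change.** In 8.3 and 8.4.2, state that claims are made outcome by outcome and that hepatic and myocardial fat are tested two-sided by Holm at an overall 0.05: the smaller p-value against 0.025 and, only if that is met, the other against 0.05. If the sponsor instead requires both outcomes for success, state that, and test each at two-sided 0.05 with no split. In 8.1, label the stated power as per outcome.

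The cost is a few sentences and no extra patients. Holm has two downsides to accept knowingly:

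- It lacks simple matching simultaneous intervals. The 97.5% intervals can still be reported (half-width 2.360 × 5.303 = 12.5, against 2.042 × 5.303 = 10.8 for 95%). However, the 97.5% interval will include zero whenever the second outcome is rejected at a p-value between 0.025 and 0.05.
- When only one outcome truly responds, the false-positive rate for the other rises from 2.5% to about 4.3–4.8%, still within the familywise 5%.
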